9.2.2. Clinical Severity and Clinical Course of RSV Infection

The following evaluations of the clinical course of RSV infection will be performed throughout the study as indicated in the [TIME AND EVENTS SCHEDULE](#):

- Clinical parameters: respiratory rate, heart rate, SpO₂, and body temperature as measured during site visits. Subjects will be provided a thermometer and asked to record body temperature in the electronic device as indicated in the [TIME AND EVENTS SCHEDULE](#).
- Evolution and severity of signs and symptoms of RSV disease as assessed by the subject on a hand-held electronic device using the RI-PRO, the RiiQ Symptom Scale (if the subject was enrolled after approval of this amendment) and additional questions about health and functioning. Symptoms reported in the RI-PRO or RiiQ Symptom Scale will not be reported as AEs but constitute a part of the efficacy evaluations. Subjects will also complete the EQ-5D-5L and the RiiQ Impact Scale (for subjects who were enrolled after approval of this amendment) on the electronic device to rate their HRQOL.
- Need for hospitalization or medically attended visits (other than the study mandated visits) during treatment and follow-up.

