As an evaluation of antiviral activity, the RSV viral load in nasal secretions, obtained via mid-turbinate nasal swab, will be measured at the central lab using a qRT-PCR assay. Mid-turbinate swab specimens for the determination of the RSV viral load will be collected at several time points during the study.

Additional information about the collection, handling, and shipment of biologic samples can be found in the laboratory manual.

If feasible, the RSV infectious virus titers as measured by quantitative culture of RSV (plaque assay) on selected nasal swab samples, may also be assessed.

Clinical Severity and Clinical Course of RSV Infection

The following evaluations of the clinical course of RSV infection will be performed throughout the study:

- Clinical parameters: respiratory rate, heart rate, SpO₂, and body temperature as measured during site visits. Subjects will be provided a thermometer and asked to record body temperature in the electronic device at home.
- Evolution and severity of signs and symptoms of RSV disease as assessed by the subject on a hand-held electronic device using the RI-PRO, the RiiQ Symptom Scale (if the subject was enrolled after approval of this amendment), and additional questions about health and functioning. Symptoms reported in the RiiQ Symptom Scale or RI-PRO will not be reported as AEs but constitute a part of the efficacy evaluations. Subjects will also complete the 5-level EuroQol 5-Dimension (EQ-5D-5L) and the RiiQ Impact Scale (for subjects who were enrolled after approval of this amendment) on the electronic device to rate their HRQOL.
- Need for hospitalization or medically attended visits (other than the study mandated visits) during treatment and follow-up.

Viral Sequencing

Viral resistance will be monitored by sequencing of the F-gene of the viral genome on all baseline samples and on post baseline samples upon request of the sponsor's protocol virologist. Other regions of

the RSV genome may also be sequenced at the request of the protocol virologist. Sequencing data will not be reported to the investigators.

PHARMACOKINETIC EVALUATIONS

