Furthermore, given that there was an unequal allocation of subjects to JNJ-53718678 and placebo in most studies and that in study 53718678RSV1002 no placebo group was included, the overall number of placebo subjects is low. Hence, this limits the ability to draw firm conclusions on the comparisons made in this section. In addition, most individual AEs and abnormalities were observed at low frequency, which further limits the comparison between JNJ-53718678 and placebo.

During clinical studies 53718678RSV1001, 53718678RSV1002, 53718678RSV1004, and 53718678RSV2001, among subjects who received at least 1 dose of JNJ-53718678, 70% experienced an AE as compared to 46.7% of all subjects who received placebo. All but 1 of the treatment-emergent AEs (TEAEs) reported during these studies were either grade 1 or grade 2 in severity; 1 subject who received placebo was reported with a grade 3 headache in study 53718678RSV1001. Adverse events observed more frequently (difference in incidence of $\geq 5\%$) in subjects who had received at least 1 dose of JNJ-53718678 compared to subjects who received

placebo included diarrhea (20.8% vs 11.1%), dysgeusia (10.8% vs 0.0%), epistaxis (7.5% vs 0.0%), fatigue (6.7% vs 0.0%), abdominal discomfort (5.0% vs 0.0%), and hot flush (5.0% vs 0.0%).

In study 53718678RSV1006, 35.7% and 31.3% of the subjects from Panel 1 and Panel 2, respectively, experienced at least one AE. In this study, all reported AEs were grade 1, and except for abdominal discomfort (reported in 2 subjects [14.3%] in Panel 1), all AEs were reported in at most 1 subject.

In study 53718678RSV1001, dysgeusia was frequently reported in subjects receiving JNJ-53718678 and in none of the subjects of the placebo group. Dysgeusia was a frequently reported AE in subjects receiving JNJ-53718678 due to the bitter taste of the oral JNJ-53718678 formulation. This observation led to the initiation of study 53718678RSV1003 to select an optimized taste of the formulation for future studies.

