1.2.4. Potential Risks

All therapies have the potential to cause adverse experiences.

During studies 53718678RSV1001, 53718678RSV1002, 53718678RSV1004, 53718678RSV1006, and 53718678RSV2001, a total of 184 adult subjects were enrolled of whom 150 received at least 1 dose of JNJ-53718678 as single doses up to 1,000 mg or multiple doses up to a total daily dose of 500 mg (as 500 mg once daily or 250 mg bid) for up to 13 days. Of those, 100 were healthy adult subjects and 50 were healthy adult subjects who were inoculated with RSV-A Memphis 37b virus. In study 53718678RSV1003, 12 subjects were enrolled but they were only to taste and not to swallow the oral solutions of JNJ-53718678.

During the ongoing study 53718678RSV1005, 44 pediatric subjects hospitalized due to RSV infection were enrolled up to the cut-off date of 6 June 2017, of whom 37 subjects received JNJ-53718678 and 7 received placebo.

Please refer to Section 1.1 for details on the reported AEs and laboratory/ECG abnormalities in the studies conducted to date.

Based upon the limited clinical data available and considering the early stage of development of JNJ-53718678, no AEs or clinically significant (non-)graded laboratory abnormalities, abnormalities in vital signs parameters, ECG abnormalities, or physical examination findings indicative of a safety concern have been identified.

Based upon the limited available clinical data, no risk related to the hepatobiliary system was identified. However, given the hepatobiliary-related nonclinical findings and because the amount of clinical data is limited, the sponsor considers hepatobiliary effects to be a safety topic of special interest and hepatobiliary function will be monitored by routine hepatobiliary function tests.

Based upon the available clinical data, no risk related to the gastrointestinal tract was identified. However, given the nonclinical findings and because the amount of clinical data is limited, any clinical signs and symptoms related to the gastrointestinal tract will be monitored during clinical studies and appropriate clinical management will be installed.

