12.3. Procedures

12.3.1. All Adverse Events

All AEs and special reporting situations, whether serious or non-serious, will be reported from the time a signed and dated ICF is obtained until completion of the subject's last study-related procedure, which may include contact for follow-up of safety. Serious AEs, including those spontaneously reported to the investigator within 30 days after the last dose of study drug, must be reported using the SAE Form. The sponsor will evaluate any safety information that is spontaneously reported by an investigator beyond the time frame specified in the protocol.

All events that meet the definition of an SAE will be reported as SAEs, regardless of whether they are protocol-specific assessments.

Signs and symptoms of RSV disease, such as rhinitis, rhinorrhea, nasal congestion, sneezing, nasopharyngitis, earache, malaise (tiredness), cough, shortness of breath and/or wheezing, muscle and/or joint pain, headache, fever, nasal blood spotting, and decreased oxygen saturation are part of the efficacy-related assessments and hence should not be reported as AEs.

All AEs, regardless of seriousness, severity, or presumed relationship to study drug, must be recorded using medical terminology in the source document and the eCRF. Whenever possible, diagnoses should be given when signs and symptoms are due to a common etiology (eg, cough, runny nose, sneezing, sore throat, and head congestion should be reported as "upper respiratory infection"). Investigators must record in the eCRF their opinion concerning the relationship of the AE to study therapy. All measures required for AE management must be recorded in the source document and reported according to sponsor instructions.

The sponsor assumes responsibility for appropriate reporting of AEs to the regulatory authorities. The sponsor will also report to the investigator (and the head of the investigational institute where required) all suspected unexpected serious adverse reactions (SUSARs). The investigator (or sponsor where required) must report SUSARs to the IEC/IRB that approved the protocol

unless otherwise required and documented by the IEC/IRB. A SUSAR will be reported to regulatory authorities unblinded. Participating investigators and IEC/IRB will receive a blinded SUSAR summary, unless otherwise specified.

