Wet or loose cough					

Felt nauseous (feeling like you wanted to throw-up)					
Stomach ache					

Please rate the extent to which you had each symptom during the past **24 hours**.

	Not at all	A little bit	Somewhat	Quite a bit	Very much
Felt dizzy					
Head congestion					
Headache					
Lack of appetite					
Sleeping more than usual					
Body aches or pains					
Weak or tired					
Chills or shivering					
Felt cold					
Felt hot					
Sweating					

In the past **24 hours**, **how often** have you had any of the following symptoms?

	Never	Rarely	Sometimes	Often	Always
Sneezing					

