Coughing					
Coughed up mucus or phlegm					

	0 times	1 time	2 times	3 times	4 or more times
How many times did you vomit?					
How many times did you have diarrhea?					

© Respiratory Infection-Patient Reported Outcome Symptom Questionnaire, adapted from the FLU-PRO questionnaire by permission of the developer.

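### The questionnaire-based AE exemption in Section 9.2.2 and the Synopsis conflicts with Sections 12.3.1 and 1.2.4, and permits under-reported and inconsistently reported non-serious gastrointestinal AEs

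*Protocol*

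**What the plan says.** Section 9.2.2 gives the rule: "Symptoms reported in the RI-PRO or RiiQ Symptom Scale will not be reported as AEs but constitute a part of the efficacy evaluations". The Synopsis repeats it under Efficacy Evaluations: "Symptoms reported in the RiiQ Symptom Scale or RI-PRO will not be reported as AEs but constitute a part of the efficacy evaluations". Neither place carves out any item.

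The RI-PRO (Attachment 2) covers more than respiratory symptoms. It includes "Felt nauseous (feeling like you wanted to throw-up", stomach ache, dizziness, "How many times did you vomit" and "How many times did you have diarrhea".

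Section 12.3.1 frames the exemption differently. It removes from AE reporting "Signs and symptoms of RSV disease, such as rhinitis, rhinorrhea, nasal congestion, sneezing, nasopharyngitis, earache, malaise (tiredness), cough" and further examples, none of which is gastrointestinal or dizziness. The same section requires all other AEs to be recorded whatever their severity, and every event meeting the SAE definition to be reported as an SAE.

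Section 9.7 exempts evaluations of RSV signs and symptoms that belong to the efficacy assessments. It restores reporting only for exacerbations of pulmonary disease, exacerbations of cardiovascular conditions, and bacterial superinfections.

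Section 1.2.4 states that "any clinical signs and symptoms related to the gastrointestinal tract will be monitored during clinical studies", citing nonclinical findings and the limited amount of clinical data.

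**The concern.** Section 9.2.2 decides whether a symptom is an AE by whether it is reported in a questionnaire. Section 12.3.1 decides by whether it is a sign or symptom of RSV disease. The two tests part company for RI-PRO items that are not typical of RSV. The sponsor acknowledges that there are many such items: the rationale for Amendment 1 says that many RI-PRO symptoms are uncommon in adults with RSV disease.

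The affected items fall in the organ system that Section 1.2.4 undertakes to watch. Section 1.1 names the gastrointestinal system as a target of toxicity in dogs and reports stomach ulceration in minipigs.

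Safety and tolerability is a secondary endpoint. Section 11.8 summarizes it through AE percentages by treatment group, and the DRC reviews the accumulating safety data. A site that follows 9.2.2 literally would leave non-serious nausea, vomiting, stomach ache, diarrhea and dizziness out of those summaries. A site that follows 12.3.1 would include them.

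**Working it through.** There is no stated figure to reproduce. The check sets the provisions side by side and follows one event through them.

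**Test case.** A subject has non-serious diarrhea that starts after the first dose.

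1. *Section 9.2.2 and Synopsis.* Diarrhea is an RI-PRO item. Read literally, it is not reported as an AE.
2. *Section 12.3.1, general duty.* All AEs are recorded. The event is recorded unless exempt.
3. *Section 12.3.1, exemption.* It covers RSV signs and symptoms. No gastrointestinal symptom is named, which favors recording. But the list is only illustrative, and the reason given is that these symptoms form part of the efficacy assessments, which could be stretched to any RI-PRO item. The section does not mention the questionnaire rule, so it does not override it.
4. *Section 9.7.* The three kinds of complication restored to AE reporting are not gastrointestinal, so this section does not settle the case.
5. *SAE rule.* It does not apply to a non-serious event. Section 1.1 reports that, in four adult studies, all treatment-emergent AEs but one (a grade 3 headache on placebo) were grade 1 or 2, and that no SAEs occurred in the adult studies. The SAE rule would therefore be expected to capture few such events.

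Steps 1 and 2 give opposite answers, and steps 3 to 5 do not resolve them. The same path applies to nausea, stomach ache, vomiting and dizziness.

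**Can the RI-PRO replace the AE record?** For subjects enrolled under Amendment 1, the Time and Events Schedule places it at screening, Day 1 and Day 8. Footnote u puts the Day 1 administration before the first dose, so Day 8 is the only post-dose one. Attachment 2 uses a recall period of 24 hours, and dosing lasts 7 days:

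- Share of the dosing period covered: 24 h / (7 × 24 h) = 1/7, about 14%.

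**Two readings of the exemption.** The text does not say which is meant.

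- *By symptom type.* Any non-serious event matching an RI-PRO item is barred. One that falls outside the Day 8 recall window would then appear in neither the AE data nor the RI-PRO data.
- *By actual entry.* Only what the subject enters in the RI-PRO is barred. Under the Amendment 1 schedule that touches about one day of on-treatment events, and the rest stay reportable.

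The RiiQ Symptom Scale falls under the same rule and is completed twice daily through Day 14. Its items (Attachment 7) are not in the text at hand, so nothing is asserted about them.

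**The case against.** The best defense is that 12.3.1 is the operative AE section. It confines the exemption to RSV disease and names no gastrointestinal symptom. The 9.2.2 sentence itself sits in a bullet about the signs and symptoms of RSV disease. Section 12 prefers open-ended verbal questioning, so AEs are not detected through the questionnaire. On this view a sensible site records the diarrhea. Much of this stands, and it is why loss of the events is not certain. It does not remove the conflict. Open-ended questioning may elicit the event, but whether it is then coded as an AE still depends on which section the site follows.

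Four stronger readings are tempting and not supported:

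- *Gastrointestinal risk drops out of the safety data.* SAEs remain reportable, sites following 12.3.1 may record the rest, and gastrointestinal events that are not RI-PRO items are untouched.
- *A count of lost events can be projected from earlier rates, such as* "diarrhea (20.8% vs 11.1"*%).* Section 1.1 attributes that imbalance most likely to one study without a placebo group and notes similar incidence on drug and placebo in the challenge study. A projection would also have to assume the by-type reading and that every site follows it.
- *Earlier studies could not separate drug from excipient.* Section 1.1 describes studies in which drug and placebo both contained HP-β-CD. It says only that the comparison is limited by few placebo subjects and low event frequencies.
- *AE rates become uninterpretable.* Allocation is randomized and double-blind, so inconsistent recording should fall similarly on all arms in expectation. The likely effect is lower absolute rates and lower sensitivity.

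Section 1.2.4 also says that the clinical data identified no gastrointestinal risk, and it reserves the label of special interest for hepatobiliary effects. The commitment is to monitor, and it should be read no more strongly than that.

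**Conclusion.** The contradiction is real and visible in the text. Section 9.2.2 and the Synopsis exempt symptoms by questionnaire. Section 12.3.1 exempts them by their link to RSV. Section 1.2.4 promises monitoring of symptoms that the first rule, read literally, takes out of AE reporting. The consequence is possible under-reporting, and differences between sites, for non-serious nausea, stomach ache, vomiting, diarrhea and dizziness.

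The extent depends on two things that the document leaves open: which section sites follow, and whether the bar applies by symptom type or by actual entry. It therefore ranges from no loss to all matching non-serious events. The finding that the RI-PRO is no substitute rests on the Amendment 1 schedule and holds only for subjects enrolled under it.

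**What to change.** Reconcile Section 9.2.2, the Synopsis, Section 9.7 and Section 12.3.1 so that one rule governs:

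- Define the exemption by a closed list of RSV signs and symptoms. The list in 12.3.1 can be the starting point, but its open-ended introduction must go; pointing 9.2.2 at the present wording would not close the gap.
- Remove the questionnaire as the criterion for exemption in 9.2.2 and the Synopsis.
- State that gastrointestinal symptoms and dizziness with onset or worsening after the first dose are recorded as AEs, even if also entered in the RI-PRO or RiiQ.

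The cost is protocol wording, a communication to sites, and some additional AE entries. Some of those will be due to RSV itself, and the placebo arm puts them in context. AEs not recorded at the time are hard to recover later, so the change is worth making while subjects are still being enrolled.

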9.2.3. Viral Sequencing

Viral resistance will be monitored by sequencing of the F-gene of the viral genome on all baseline samples and on post baseline samples upon request of the sponsor's protocol virologist. Other regions of the RSV genome may also be sequenced at the request of the protocol virologist. Sequencing data will not be reported to the investigators.

Changes in viral sequence will be evaluated but will not be reported as AEs.

9.3. Pharmacokinetics

Pharmacokinetic assessment during the study will be based on sparse sampling and will be performed using a popPK approach by means of nonlinear mixed-effects modeling.

Venous blood samples for determination of JNJ-53718678 plasma concentrations will be collected at the time points indicated in the [TIME AND EVENTS SCHEDULE](#). Samples can also be used for the analysis of metabolites of JNJ-53718678, excipients (eg, hydroxypropyl- β -cyclodextrin), protein binding, or endogenous markers for enzymes or transporters involved in the metabolism and distribution of JNJ-53718678, at the discretion of the sponsor. Blood samples collected for pharmacokinetics may additionally be used to evaluate safety or efficacy aspects that address concerns arising during or after the study period. Genetic analyses will not be performed on these samples. Subject confidentiality will be maintained.

Samples will be analyzed (applicable treatment groups only [not the placebo group]) to determine concentrations of JNJ-53718678 using a validated, specific and sensitive method under the supervision of the sponsor.

Based on the individual concentration-time data, using the actual dose taken and the actual sampling times, pharmacokinetic parameters and exposure information of JNJ-53718678 will be

derived using popPK modelling, including, but not limited to: AUC, C_{trough} , and possibly C_{max} . Baseline covariates (eg, body weight, age, sex, creatinine clearance, race) may be included in the model, if relevant. Other pharmacokinetic parameters may be determined at the discretion of the sponsor if deemed useful to evaluate the pharmacokinetics of the analytes in scope. If deemed useful to evaluate the safety or efficacy of JNJ-53718678, popPK modeling of other analytes (eg, excipients) may be performed at the discretion of the sponsor.

The following times need to be recorded on the requisition form and/or the study medication log: date and time of study drug intake, date and time of pharmacokinetic blood sampling, and time of meal if any in the time window of 2 hours before and 2 hours after study drug intake on the day of pharmacokinetic sampling.

9.4. Pharmacokinetic/Pharmacodynamic Evaluations

Obtained pharmacokinetic and pharmacodynamic data (selected antiviral activity parameters, clinical outcomes, and safety parameters) will be used to explore the relationship between the pharmacokinetics and pharmacodynamics.

9.5. Biomarkers

Blood samples for host mRNA assessment will be collected at time points indicated in the [TIME AND EVENTS SCHEDULE](#) and may be used for exploratory biomarker analyses (eg, proteins including cytokines), on the premise that these markers may play a role in the treatment response, safety or pharmacokinetics of JNJ-53718678, or RSV-related disease. Leftover mid-turbinate nasal swabs and blood samples collected for other testing may be used as well for the same purpose. Analyses of biomarkers will be conducted at the sponsor's discretion and may be reported separately from this study.

9.6. Medical Resource Utilization

Medical resource utilization data will be collected in the eCRF for all subjects throughout the study at time points indicated in the [TIME AND EVENTS SCHEDULE](#). Protocol-mandated procedures, tests, and encounters are excluded. The data collected will include:

- Number and duration of medical care encounters: hospitalizations, physician or emergency room visits, test, and procedures, including surgeries, and other procedures (inpatient and outpatient) for RSV infection or complications associated with RSV per investigator assessment.

9.7. Safety Evaluations

Safety and tolerability will be evaluated throughout the study from signing of the ICF (including diagnostic ICF, if applicable) onwards until the last study-related activity (end of study/early withdrawal).

Details regarding the DRC are provided in [Section 11.9](#).

Any clinically relevant changes occurring during the study must be recorded on the AE section of the eCRF.

Any clinically significant abnormalities persisting at the end of the study/early withdrawal will be followed by the investigator until resolution or until a clinically stable endpoint is reached.

The study will include the following evaluations of safety and tolerability according to the time points provided in the [TIME AND EVENTS SCHEDULE](#):

Adverse Events

Adverse events will be reported by the subject (or, when appropriate, by a caregiver, surrogate, or the subject's legally acceptable representative) for the duration of the study. Adverse events will be followed by the investigator as specified in Section 12. Grading will be determined according to the criteria specified in the DMID adult toxicity tables (see [Attachment 1](#)).

Special attention will be paid to those subjects who discontinue the study for an AE, or who experience an AE of at least grade 3, or an SAE.

Exacerbations of underlying pulmonary disease (eg, asthma, COPD) occurring after treatment start, bacterial superinfections of presumed respiratory origin per investigator assessment, and exacerbations of underlying cardiovascular conditions should be reported as AE and are considered events of interest (complications associated with RSV per investigator assessment). Further details on these events of interest will be captured separately in the eCRF.

Evaluations of signs and symptoms of RSV disease that are part of the efficacy evaluations (with exception of the complications mentioned above) will not be reported as AEs.

Clinical Laboratory Tests

Blood samples for serum chemistry and hematology and a urine sample for urinalysis will be collected at time points indicated in the [TIME AND EVENTS SCHEDULE](#) and analyzed at the central laboratory. The investigator must review the laboratory results, document this review, and record any clinically relevant changes occurring during the study in the AE section of the eCRF. Laboratory reports must be filed with the source documents.

In case a grade 3 or grade 4 laboratory abnormality occurs, a confirmatory test must be performed preferably within 48 hours but no later than 72 hours after the results have become available.

Any values that indicate a potential safety concern will be assessed by the investigator and appropriate follow-up actions, including potential discontinuation from treatment, will be carried out.

The following tests will be performed by the central laboratory:

- Hematology Panel
 - hemoglobin
 - hematocrit
 - RBC count
 - WBC differential:
 - * neutrophils
 - * lymphocytes

- | | |
|-------------------------------------|-----------------|
| -reticulocyte count | * monocytes |
| -RBC parameters: | * eosinophils |
| * mean corpuscular hemoglobin (MCH) | * basophils |
| * MCH concentration | -platelet count |
| * mean corpuscular volume | |
| -WBC count | |

Note: A WBC evaluation may include any abnormal cells, which will then be reported by the laboratory. An RBC evaluation may include abnormalities in the RBC count, RBC parameters, or RBC morphology, which will then be reported by the laboratory. In addition, any other abnormal cells in a blood smear will also be reported.

- Coagulation parameters: PT, aPTT and international normalized ratio
- Serum Chemistry Panel

- | | |
|-----------------------|--|
| -alkaline phosphatase | -glucose |
| -ALT | -potassium |
| -AST | -sodium |
| -bicarbonate | -total bilirubin (direct and indirect) |
| -uric acid | -urea |
| -chloride | -phosphorus |
| -magnesium | -calcium |

- Urinalysis

Dipstick

- specific gravity
- pH
- glucose
- protein
- blood
- ketones
- bilirubin
- urobilinogen
- nitrite
- leukocyte esterase

Sediment (if dipstick result is abnormal)

- RBC
- WBC
- epithelial cells
- crystals
- casts
- bacteria

Dipstick will be performed per the [TIME AND EVENTS SCHEDULE](#). If dipstick result is abnormal, flow cytometry or microscopy will be used to measure sediment. In case of discordance between the dipstick results and the flow cytometric results, the sediment will be examined microscopically.

In the microscopic examination, observations other than the presence of WBC, RBC and casts may also be reported by the laboratory.

- Renal function testing:
 - Serum creatinine and estimated Glomerular Filtration Rate (eGFR) based on creatinine by Cockcroft-Gault formula²⁵
 - Serum cystatine C and eGFR based on cystatine C²⁵

- Urinary creatinine, albumin, *N*-acetyl- β -glucosaminidase, β_2 -microglobulin, urinary phosphorus, sodium, potassium, and calcium (spot urine sample)
- Urine pregnancy testing for all women

Electrocardiogram

Twelve-lead triplicate ECGs will be collected at the time points specified in the [TIME AND EVENTS SCHEDULE](#) and when clinically indicated.

Central ECG readings will be performed by a central ECG lab. Instructions for ECG acquisition and ECG transmission will be described in the manual provided by the ECG lab. There will be 2 ECG reports: a preliminary report and a final report. Both ECG reports generated by the central ECG lab will need to be interpreted for clinical significance, signed and dated by the investigator, and filed in the subject's medical record. Clinically relevant abnormalities occurring during the study should be recorded by the investigator in the AE section of the eCRF.

During the collection of ECGs, subjects should be in a quiet setting without distractions (eg, television, cell phones). Subjects should rest in a supine position for at least 5 minutes before ECG collection and should refrain from talking or moving arms or legs.

In the event that an invasive procedure such as a blood draw or nasal aspirate and an ECG are required at the same time, ECGs should be collected first. Electrocardiograms may be repeated at the investigator's discretion to account for erroneous readings.

At each time point at which triplicate ECGs are required, 3 individual ECG tracings should be obtained as closely as possible in succession, but no more than 2 minutes apart. The full set of triplicates should be completed in less than 4 minutes.

Vital Signs

Systolic and diastolic blood pressure are to be collected at the time points specified in the [TIME AND EVENTS SCHEDULE](#).

Blood pressure measurements will be assessed in a sitting or supine position (same position at each measurement) with a completely automated device. Manual techniques will be used only if an automated device is not available.

Blood pressure measurements should be preceded by at least 5 minutes of rest in a quiet setting without distractions (eg, television, cell phones).

Clinically relevant abnormalities occurring during the study should be recorded by the investigator in the AE section of the eCRF.

Physical Examination

A physical examination (including height [only at screening] and body weight measurements) and skin examination will be performed at the visits indicated in the [TIME AND EVENTS SCHEDULE](#).

A skin examination includes an examination of the mucous membranes, but does not include a vaginal or rectal examination. However, if the subject develops a cutaneous reaction/rash, vaginal and rectal examinations may be done if clinically relevant.

Any clinically relevant changes occurring during the study must be recorded in the AE Section of the eCRF.

Specific Toxicities

Rash

In case there are skin changes, a correct diagnosis has to be made by the investigator or a dermatologist, preferably within 24 hours of detection. If a diagnosis of rash is made, the investigator will discuss this with the sponsor, preferably within 24 hours of the investigator's awareness of the rash. An assessment of severity grade should be made using the criteria specified in the DMID adult toxicity tables (see [Attachment 1](#)).

If the rash is considered to be most likely due to RSV, concomitant illness or non-study medication, standard management, including discontinuation of the likely causative agent, should be undertaken.

If a causal relationship between the rash and the study drug is reasonably suspected, then the visits and assessments will be performed as indicated in [Attachment 5](#). Unscheduled follow-up visits for close follow-up of rash will be performed based on the grade (severity) of the rash. At the investigator's discretion, additional visits and assessments can be performed.

AST and ALT Evaluation

Management will be at the discretion of the investigator and should follow generally accepted medical standards.

For grade 3 or 4 laboratory abnormalities, subjects should have a confirmatory measurement, preferably within 48 hours after the laboratory results become available to the site. This management scheme is for confirmed laboratory abnormalities and not for isolated events.

Grade 1 (1.1 to <2.0 x upper limit of normal [ULN]), or Grade 2 (>2.0 to ≤3.0 x ULN)

Subjects may continue the intake of study drug.

Subjects should be followed until resolution (return to baseline) or stabilization of AST/ALT elevation (to be agreed upon with the sponsor).

Grade 3 (>3.0 to 8.0 x ULN), or Grade 4 (>8.0 x ULN)

Subjects will permanently discontinue the intake of study drug.

It is recommended that the investigator contacts the sponsor to discuss the case. Subjects should be followed until resolution (return to baseline) or stabilization of AST/ALT elevation.

